**6.2      Visit 1**

Routine medical history and demographics and physical exam will be performed during the visit (standard care).

**6.2.1 Research blood and urine collection & handling OPTIONAL**

Research blood and urine may be collected after signing informed consent (OPTIONAL). Approximately 50 mL or 3.5 tablespoons of blood will be taken from a peripheral vein or an indwelling catheter if present and functional specifically for research studies. Study staff will then provide a urine specimen cup and self-catch instruction to the participant. The participant will be able to do this in the privacy of the clinic restroom.

If collected, research blood and urine specimens will be transported to our lab in the STRF in approved containers by qualified personnel. Additional blood will be collected as needed for initial eligibility screening. Urine will be processed by centrifugation and the supernatant will be stored separately from the pellet. Both blood and urine samples are de-identified in the lab per HIPAA protocol.

Baseline symptoms questionnaires will also be administered.

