**6.1      Recruitment**

Participants will be recruited through the urology outpatient clinics at the Medical Arts and Research Center (MARC). Attending physicians in the Department of Urology, and selected other personnel who also serve as research staff for this study, will identify prospective study participants. To eliminate selection bias, any patient who presents with invasive bladder cancer and meets the inclusion/exclusion criteria will be given an option to participate in the study. The inclusion of participants or refusal to participate by patients eligible for this study will in no way compromise the quality of health care they will receive.

**Study eligibility** will be determined by investigators and study staff with legitimate access to patient PHI due to their clinical role and/or as members of the research team. Patients who meet the eligibility criteria will be approached by one of the investigators or other members of the study staff to determine whether they are willing to participate in the study. Prior to study entry, the study staff will explain to each potential subject the research objectives, risks and benefits of study participation, alternative treatments available, and the subjects' rights and responsibilities. If the patient agrees to participate, informed consent will be obtained. Research blood and urine may be obtained- OPTIONAL (details in 6.2). Baseline symptoms questionnaires will be administered.

Patients will be approached in a private consult room located within the GU clinic at the MARC. Usual privacy policy practices will be followed. The study procedures and objectives will be described to them and they will be given a copy of the consent document. Participants will also be given contact information for someone they can call with any questions that may arise.

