### 6.3 Neoadjuvant Intravesical BCG Instillation

Prior to undergoing routine radical cystectomy (standard care), participant will receive 3 to 6 weeks of neoadjuvant intravesical BCG instillation weekly as part of the research study procedure. The instillation will be scheduled roughly one week apart pending on the clinic's and participant's schedules, and also participant's reaction to the BCG instillation. BCG Week 1 may occur on the same day as Visit 1.

Intravesical BCG will be given as the intervention measure for treatment of bladder cancer. In brief, following sterile preparation, a Foley catheter is introduced into the bladder thru the urethral meatus. The BCG is instilled through gravity drainage and held in the bladder for approximately 2 hours. Instructions are provided to the patient regarding the proper disposal of the BCG. The duration of BCG treatment is allowed to fluctuate between 3-6 weeks for two reasons: (1) This allows for flexibility in scheduling participants for radical cystectomy as the time from enrollment to cystectomy would vary based on surgeon and patient preferences and on operative room availability. In this manner, the surgery date can be established first and then duration of treatment would be based on amount of time available between enrollment and cystectomy date. In our experience, this "time period" is usually 4-6 weeks; (2) The number of BCG treatments needed to elicit expected immune responses is not known. In fact the current paradigm of 6 weekly treatments has little scientific justification but was based on a rather arbitrary dosing schedule; (3) Allowing for multiple durations of therapy, could provide us with the opportunity to explore differences in immune responses across different dosing duration regimens.

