## 7.0 Study Calendar

Study Component/Procedures	Visit 1	BCG Week 1 (may be same day as Visit 1)	BCG Week 2	BCG Week 3	BCG Week 4 a	BCG Week 5 a	BCG Week 6 a	Cystectomy	Post Cystectomy (~within 90 days post cystectomy)
Informed Consent	R								
Medical History, Demographics, Physical Exam	S								
Assessment of AEs		R	R	R	R	R	R		
Urinary symptoms questionnaires	R	R	R	R	R	R	R		
Blood Collection	R*							R	R
Urine Collection (pre and post treatment urine collected on BCG weeks)	R*	R	R	R	R	R	R		
Tissue collection								R	
Tissue blocks from cystectomy procedure								R	

"R" indicates performed only for research purposes and "S" indicates performed for standard care practice

a- Additional BCG treatments beyond week 3 will be given selectively to participants based on time interval between study enrollment and scheduled cystectomy date

\* Optional blood and urine collection

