## 8.0 Criteria for Evaluation and Endpoint Definitions

- 8.1 The primary end-point is taken as difference in tumor-specific immune response (comparing before and after treatment with BCG). Tumor-specific immune response will be measured using a standard T cell proliferation assay. T cell response to autologous tumor will be measured using a paired analysis by utilizing PBMCs collected before and after BCG therapy. Autologous monocyte-derived dendritic cells (moDCs) and autologous T cells will be co-cultured following pulsation of moDCs with whole tumor lysates.
- 8.2 Secondary endpoints are exploratory and will not be considered for determining sample size. Secondary endpoints include (1) description of tumor infiltrating lymphocyte populations following BCG (examining 3 weeks of treatment versus 4,5, or 6 weeks as available); (2) determination of the presence/absence of BCG in lymph nodes following treatment; (3) examining extent of necrosis/apoptosis in tumor following BCG treatment; (4) pathologic assessment of tumor stage following BCG treatment; (5) characterization of systemic immune populations before treatment, at time of cystectomy,

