## 9.0 Statistical Considerations

### 9.1 Sample Size Determination

This is a one-arm open label study of the tumor-specific immune effect of BCG in participants undergoing radical cystectomy for bladder cancer. The sample size calculation is based on one-sided testing on the proportion of subjects who experience an increase in T cell proliferation ( $\geq 100\%$  increase in proliferative index during the proliferation assay) in post treatment assessment compared to pretreatment assessment with power=90% and target alpha=5%. The null proportion responding is taken to be 0.10 and the desired proportion responding is specified as greater than or equal to 0.50. The estimated sample size, under these assumptions, is 10. In order to achieve this number

we would need to consent 25 participants to account for completion rate and assay variability.

Sample size calculations were run using Stata 10.1 (College Station, Texas).

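### The primary endpoint needs a blood sample taken before BCG, but the only scheduled pre-BCG research draw is optional

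*Combined protocol and SAP*

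**What the plan says.** **What the endpoint needs.** Section 8.1 states: "T cell response to autologous tumor will be measured using a paired analysis by utilizing PBMCs collected before and after BCG therapy". Section 9.1 calls a participant a responder if the proliferative index rises by at least 100% "in post treatment assessment compared to pretreatment assessment".

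**When blood is taken.**
- Visit 1, section 6.1: "Research blood and urine may be obtained- OPTIONAL (details in 6.2".
- Visit 1, section 6.2.1: "Research blood and urine may be collected after signing informed consent (OPTIONAL". Its heading also carries the word optional.
- Visit 1, calendar (section 7.0): the blood entry has an asterisk, footnoted "Optional blood and urine collection".
- BCG Weeks 1 to 6: the calendar marks no blood, and section 6.3.1 covers urine only.
- Cystectomy (6.4) and follow-up visit (6.5): research blood is to be collected, with no optional label. Both draws come after BCG.

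**Other relevant text.** Section 6.2.1 also mentions screening blood: "Additional blood will be collected as needed for initial eligibility screening". Section 6.3 adds: "BCG Week 1 may occur on the same day as Visit 1". On numbers, section 9.1 requires 10 and says "we would need to consent 25 participants to account for completion rate and assay variability".

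**The concern.** The specimen that defines the primary endpoint has weaker status than specimens that do not. Blood at cystectomy and urine before BCG are to be collected; blood before BCG only may be. Once the first instillation is given, a true baseline cannot be recovered and no analysis can restore it.

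Three things are at stake:

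- The evaluable number may fall below the 10 on which the trial was sized.
- Those who volunteer a baseline sample may differ from those who do not, so the responder proportion may describe a selected subset.
- Some participants would receive BCG as a research procedure without being able to contribute to the trial's primary question.

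The fifth secondary endpoint in section 8.2, systemic immune populations before treatment and at cystectomy, depends on the same draw.

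**Working it through.** **1. Can a compliant participant be unclassifiable?**

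- Classification needs the post-BCG index divided by the pre-BCG index, with the threshold at a ratio of 2 (a 100% increase). Without the denominator there is no classification.
- The only scheduled source of the denominator is Visit 1 blood, optional in all three places that mention it.
- The screening blood in 6.2.1 is taken as needed and is not designated for PBMCs or research.
- The eligibility criteria (section 5.0) do not ask for a baseline sample. Section 9.0 has no rule for a missing baseline, for replacement or for an evaluable population.
- When Visit 1 and BCG Week 1 share a day, section 8.1 implies that blood comes first, but no procedural step says so.

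So the answer is yes, from the text alone and without any assumed rate.

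**2. The plan's own figure**

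Inputs from section 9.1: null proportion p0 = 0.10, alternative p1 = 0.50, one-sided alpha 0.05, power 0.90. With the normal approximation,

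n = [(1.645 × √(0.10 × 0.90) + 1.282 × √(0.50 × 0.50)) / 0.40]² = 8.04, so 9.

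The one-sided arcsine formula gives 9.96 (10), the continuity-corrected one-sided formula 10.39 (11), and the two-sided normal formula 9.44 (10). The stated 10 is reproduced within this range. The allowance is 10/25 = 40% evaluable, a loss of 60%.

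**3. What missing baselines would do**

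Let e be the share otherwise evaluable and d the share of those without a baseline sample. Only e = 0.40 has an anchor in the plan (10/25); e = 0.60 and every d are assumptions. The evaluable number is N ~ Binomial(25, e(1 − d)). Average power is the sum over N of P(N) times the exact one-sided 5% binomial power at that N.

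| e | d | Expected N | P(N ≥ 10) | Average power | Loss against d = 0 (points) |
|---|---|---|---|---|---|
| 0.40 | 0 | 10 | 58% | 83.6% | – |
| 0.40 | 0.05 | 9.5 | 49% | 81.7% | 2 |
| 0.40 | 0.10 | 9 | 41% | 79.6% | 4 |
| 0.40 | 0.20 | 8 | 26% | 74.7% | 9 |
| 0.40 | 0.30 | 7 | 13% | 68.6% | 15 |
| 0.40 | 0.50 | 5 | 2% | 52.5% | 31 |
| 0.60 | 0 | 15 | 99% | 95.3% | – |
| 0.60 | 0.05 | 14.25 | 97% | 94.3% | 1 |
| 0.60 | 0.10 | 13.5 | 95% | 93.1% | 2 |
| 0.60 | 0.20 | 12 | 84% | 89.8% | 6 |
| 0.60 | 0.30 | 10.5 | 65% | 85.3% | 10 |
| 0.60 | 0.50 | 7.5 | 19% | 71.8% | 24 |

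Losses are measured against the d = 0 row, not against the stated 90%. Exact power at n = 10 is 82.8% even with no missing baselines (at least 4 responders, alpha 0.013), and that shortfall is a separate matter.

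**4. How much slack there is**

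Expected N stays at 10 while 25e(1 − d) ≥ 10, that is d ≤ 1 − 0.40/e. For e = 0.40, 0.50, 0.60 and 0.80 this allows d up to 0, 0.20, 0.33 and 0.50.

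**The case against.** The strongest reply is that consenting 25 to obtain 10 already leaves generous room. Section 9.1 gives completion rate and assay variability as the reasons, and completion could be read as completing both blood draws. The documents do not split the 60% between causes, so this reading cannot be excluded. If it is right, the e = 0.40 rows overstate the loss. At e = 0.80, even 30% missing baselines leave power at about 94%.

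Other points also stand in part:

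- If only 5% to 10% lack a baseline, the cost is about 1 to 4 power points at e = 0.40 or 0.60.
- Exact power is not monotone in n: 85.5% at 8, 74.6% at 9 and 82.8% at 10. Falling just short of 10 is therefore a crude measure of harm.
- If very few people would refuse a mandatory draw, refusals cannot explain 20% to 50% missing. Shares that large would need logistical causes, or would mean a real loss of enrolment once the draw is mandatory.
- No evidence in the documents shows that selection would occur; it is a possibility.

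These points limit the numerical illustration. They do not alter the fact that the protocol permits treatment without the sample that the endpoint requires. Spare numbers protect the count only. They neither prevent selection nor stop BCG being given to participants who cannot be classified.

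**Conclusion.** The concern holds, with high confidence, and must be fixed. The contradiction between a paired before/after endpoint and an optional before sample is established by the text and rests on no assumption. Its size cannot be derived from the documents. Over assumed missing shares of 5% to 50%, the loss of average power runs from about 2 to 31 points if 40% are otherwise evaluable, and from about 1 to 24 points if 60% are. The severity rests on the irrecoverable gap in the sole primary endpoint, not on any one of these figures.

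**What to change.** - Drop the optional wording for Visit 1 research blood in sections 6.1 and 6.2.1, and the asterisk on blood in the calendar. Visit 1 urine can stay optional.
- Require the 50 mL draw from every participant before the first instillation, stated explicitly for a same-day Visit 1 and BCG Week 1.
- State in section 9.0 that a participant without a usable pre-BCG PBMC sample does not count toward the 10.

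A replacement rule on its own would protect the number, but not against selection or against treating participants who cannot be classified.

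**Cost.** Protocol text and matching consent text; the draw is already scheduled, so no procedure is added. People unwilling to give baseline blood would not enrol, so recruitment may have to run longer to replace them. Their data would also be lost to the four secondary endpoints that need no baseline blood: tumor-infiltrating lymphocytes, BCG in lymph nodes, necrosis/apoptosis and pathologic stage.

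**Limit.** The change does not guarantee evaluability. Under section 6.4 no research bladder tissue is taken when there is too little excess tumor, and the assay needs tumor lysate.

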### 6.3 Neoadjuvant Intravesical BCG Instillation

Prior to undergoing routine radical cystectomy (standard care), participant will receive 3 to 6 weeks of neoadjuvant intravesical BCG instillation weekly as part of the research study procedure. The instillation will be scheduled roughly one week apart pending on the clinic's and participant's schedules, and also participant's reaction to the BCG instillation. BCG Week 1 may occur on the same day as Visit 1.

Intravesical BCG will be given as the intervention measure for treatment of bladder cancer. In brief, following sterile preparation, a Foley catheter is introduced into the bladder thru the urethral meatus. The BCG is instilled through gravity drainage and held in the bladder for approximately 2 hours. Instructions are provided to the patient regarding the proper disposal of the BCG. The duration of BCG treatment is allowed to fluctuate between 3-6 weeks for two reasons: (1) This allows for flexibility in scheduling participants for radical cystectomy as the time from enrollment to cystectomy would vary based on surgeon and patient preferences and on operative room availability. In this manner, the surgery date can be established first and then duration of treatment would be based on amount of time available between enrollment and cystectomy date. In our experience, this "time period" is usually 4-6 weeks; (2) The number of BCG treatments needed to elicit expected immune responses is not known. In fact the current paradigm of 6 weekly treatments has little scientific justification but was based on a rather arbitrary dosing schedule; (3) Allowing for multiple durations of therapy, could provide us with the opportunity to explore differences in immune responses across different dosing duration regimens.

#### 6.3.1 Research Urine Collection and Handling Pre and Post-BCG Instillation (research only)

We will collect a urine sample pre-BCG treatment. We will also collect urine samples post-BCG instillations, specifically the second void, which typically occur 4-6 hours post Intravesical BCG treatment. Participants will be given the following options for collection of urine sample post intravesical BCG treatments:

- a) Participant may remain in the clinic for urine collection  
-OR-
- b) Participant may leave the clinic with a urine sample collection cup and biohazard bag. Participant will be given specific instruction to collect second void post intravesical BCG therapy, and return the sample to the clinic.

Study team member will work with participant on how post BCG therapy urine will be collected and returned to the team. Post-BCG urine collection will take place at weekly during the 3-6 weeks of intravesical BCG treatments. Urine will be processed by centrifugation and the supernatant will be stored separately from the pellet.

#### 6.3.2 Dose Modification and Toxicity

BCG at a dose of 1 to 8 x 10^8 is given intravesically for 2 hours, irrespective of weight or age. This dose was chosen because previous experience and standard care with BCG.

Adjustments (1/2 strength or 1/4 strength) are allowed for participants demonstrating poor toleration of treatment as is done in the course of usual standard care.

\*Note: Due to the nationwide shortage of BCG, the entire vial (1 full dose) may not be used for the treatment. Patients may elect to receive BCG treatments at standard of care physician.

BCG treatment may be held by the treating physician for clinical reasons such as active urinary tract infection or gross bleeding from the bladder as per standard care.

Regardless of dose or amount of BCG given, patients will be allowed to continue with study procedures.

#### 6.3.3 Monitoring during BCG Instillation

At each visit (including baseline) symptom questionnaires will be administered prior to any procedures. The symptom questionnaires will assess irritative LUTS present. If BCG Grade 3 bladder toxicity occurs it will result in postponing combined therapy by 1 week, provided that the patient's symptoms resolved.

Participant-reported side effect questionnaires will be administered prior to each weekly instillation to ascertain the previous instillation's effects. Patients will be monitored in the clinic during instillation of BCG.

Adverse event (AE) monitoring will be assessed at each clinic visit, during BCG treatments, and on the day of cystectomy. Safety will be assessed by a urologist with training in administration of intravesical BCG.

**Dose-Limiting Toxicity (DLT)** - Dose-limiting toxicity (DLT) is defined as any grade 3 or 4 systemic toxicities or evidence of grade 4 bladder toxicity using the National Cancer Institute common toxicity criteria.

#### 6.4 Research Blood, urine, & tissue collection (research only) at the time of Radical Cystectomy (standard care)

Research blood and urine will be collected at radical cystectomy.. Approximately 50 mL or 3.5 tablespoons of blood will be taken from a peripheral vein or an indwelling catheter if present and functional specifically for research studies. The handling method can be found in Section 6.2.1. Voided urine or urine from an indwelling catheter will be collected.

At the time of radical cystectomy, a section of tumor tissue, normal adjacent bladder tissue, and adjacent lymphatic tissue will be taken for immune studies. A small section of the tissue from the bladder (approximately 5 mm x 5 mm x 5 mm) will be taken. Most patients with muscle invasive tumors have large tumors so taking a small section does not compromise pathologic assessment of stage. This research tissue would be excess tumor and would not compromise the ability of the pathologist to stage or grade the tumor, and poses no additional meaningful risk to the patient. To ensure this we clarify that the tumor tissue taken for research represents a small (10% of the tumor volume or less) component of the tumor. If sufficient excess tumor is not available for research purposes, then no research bladder tissue would be removed. We have experience with such post-treatment tumor acquisition for research in bladder cancer studies here at UTHSCSA. For benign adjacent bladder mucosa, we will also take a small section (approximately 5 mm x 5 mm x 5 mm) of tissue. Normally for lymph node dissections, we typically remove 20-60 lymph nodes during a cystectomy. We will isolate several (2-8) lymph nodes to be used for research purposes. The lymph node will removed and then surgically split in half. One half will be sent for pathologic processing and the other half will be used for research. In this way, we do not compromise the ability to pathologically examine the lymph nodes.

We will also obtain the tissue blocks from cystectomy on all subjects from pathology where surgery was done.

6.5 Post-Radical Cystectomy Follow-up Visit (standard care)

As per routine care, participants will return to clinic approximately within 90 days following surgery for a follow-up visit. During this visit, research blood will be collected.

Approximately 50 mL or 3.5 tablespoons of blood will be taken from a peripheral vein or an indwelling catheter if present and functional specifically for research studies. The research blood specimens will be transported to our lab in the STRF in approved containers by qualified personnel. The blood sample will be de-identified in the lab per HIPAA protocol.

## 7.0 Study Calendar

Study Component/Procedures	Visit 1	BCG Week 1 (may be same day as Visit 1)	BCG Week 2	BCG Week 3	BCG Week 4 a	BCG Week 5 a	BCG Week 6 a	Cystectomy	Post Cystectomy (~within 90 days post cystectomy)
Informed Consent	R								
Medical History, Demographics, Physical Exam	S								
Assessment of AEs		R	R	R	R	R	R		
Urinary symptoms questionnaires	R	R	R	R	R	R	R		
Blood Collection	R*							R	R
Urine Collection (pre and post treatment urine collected on BCG weeks)	R*	R	R	R	R	R	R		
Tissue collection								R	
Tissue blocks from cystectomy procedure								R	

"R" indicates performed only for research purposes and "S" indicates performed for standard care practice

a- Additional BCG treatments beyond week 3 will be given selectively to participants based on time interval between study enrollment and scheduled cystectomy date

\* Optional blood and urine collection

